- Adverse event which requires discontinuation of the treatment regimen or results in inability to comply with study procedures
- Discretionary decision by the site investigator

-
- At the discretion of the IRB, FDA, NIH, or other government agencies as part of their duties to ensure that research subjects are protected, or the industry supporter or its designee
 - Study is terminated

Subjects who receive MetroGel, but do not complete the full MetroGel treatment, do not return for the Enrollment visit, or are otherwise found ineligible to be randomized to study treatment will not be enrolled into the study and will not be followed for safety or for AEs.

All randomized subjects who are discontinued from receiving further study product will continue to be followed through Visit 7 (Week 24, Day 168).

If withdrawal of consent or study product discontinuation occurs after study treatment is initiated, the subject will be asked to continue scheduled study procedures including safety evaluations, if possible, and be given appropriate care under medical supervision if symptoms of any AE related to participation in the study are continuing. The subject will be followed until the AE is resolved or until the subject's condition becomes stable.

Subjects who withdraw their consent for further participation in the study after their study treatment ends or discontinue study product early will be reminded of the importance of continuing in the study for safety evaluations. Subjects will be encouraged to complete the Early Termination evaluations if they choose not to complete the remaining study visits.

Subjects who enroll in the study but do not return for study visits after a minimum of three attempts to contact them over a 2-week period will be considered lost to follow-up.

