5. SAMPLE SIZE CONSIDERATIONS

Sample size calculations are based on the assumption of detecting a 50% reduction in the cumulative proportion of subjects who experience BV recurrence by 12 weeks post-administration of study product among subjects receiving LACTIN-V compared to those receiving placebo in a complete case analysis at the 0.05 significance level. The proportion of subjects among controls who will experience BV recurrence at 12 weeks is assumed to be 30%. We assume a LACTIN-V to placebo allocation ratio of 2:1 and 10% of subjects drop-out from the Complete Case population. Given logistical and feasibility constraints on the sample size and that this is a Phase II-b trial, which will provide screening evidence about safety and efficacy for a subsequent Phase III trial, this trial is powered at the 70% level. Given the assumptions above, a sample size of 228 subjects is required to detect a 50% reduction in the cumulative proportion of subjects experiencing recurrence in the Complete Case population with 70% power using the Pearson Chi-Square test.

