6. GENERAL STATISTICAL CONSIDERATIONS

6.1. General Principles

Tabulations will be used extensively to summarize the data. All continuous variables will be summarized using the following descriptive statistics: n (sample size), mean, standard deviation, median, maximum, and minimum. The frequency and percentages (based on the sample size) of observed levels will be reported for all categorical measures. Wilson confidence intervals for binomial proportions and differences in binomial proportions will be computed for efficacy variables. Blaker confidence intervals for binomial proportions and differences in binomial proportions will be computed for safety variables. For the hypothesis tests comparing treatment groups with respect to safety outcomes, the two-sided Fisher's Exact test will be used. For the hypothesis tests comparing treatment groups with respect to efficacy outcomes, the two-sided Chi-Square test will be used. For all tests, a 5% two-sided significance level will be used.

For all efficacy outcome measures, the Complete Case population (see Section 6.3) will be used as the primary analysis population and the Per Protocol, modified Intent-to-Treat, and Intent-to-Treat populations will be used as secondary analysis populations. For all safety analyses, the Safety population will be used as the analysis population.

All summary tables will be structured with a column/sub-table for each treatment group (LACTIN-V, Placebo, and All Subjects). In general, all data will be listed by treatment group and/or subject, and when appropriate by visit number within subject. The total population size relevant to that table/column if applicable, including any missing observations will be displayed in the tables.

Note that in the data listings, Subject ID is the unique subject identifier, not the Study ID used on study and dates will not be included, only Study Day. Study Day 1 will be the day of the first dose of treatment.

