As an additional analysis of the outcome measures of BV recurrence by Visit 4 and by Visit 7, the median time to BV recurrence (from randomization) will be estimated by treatment group using Kaplan-Meier estimates ([Table 17](#) and [Table 18](#)). In addition, the median 95% confidence interval, minimum, first quartile, third quartile, and maximum estimates of time to BV recurrence will be presented. For subjects who experience BV recurrence by Visit 4 (Week 12), the time of BV recurrence will be defined as the midpoint between the earliest time point of a positive BV diagnosis (post-baseline) and the previous observed time point. For subjects without BV recurrence at or before Visit 4, the BV recurrence endpoint will be coded as censored, with time to recurrence defined as the elapsed time from the first dose of study product, to the Visit 4 time point, or to the first occurrence of loss to follow-up or the time-point at which the subject became ineligible for the particular analysis population. Time to BV recurrence by Visit 7 (Week 24) will be defined similarly. The analyses will be performed in the ITT, mITT, CC, and PP populations, where the ITT and mITT summaries will be replicated using the imputation methods described in Section 6.5. Kaplan-Meier curves for BV recurrence will also be generated for each analysis population by Visit 4 (Week 12) and by Visit 7 (Week 24), respectively ([Figure 2](#) and [Figure 3](#)).

As a sensitivity analysis of the outcome measures of BV recurrence by Visit 4 and by Visit 7, the cumulative proportion of BV recurrence analyses will be repeated in the mITT and CC populations after removing the subjects who received additional treatment for BV as documented in the concomitant medications CRF after the beginning of administration of LACTIN-V or placebo and before Visit 4 and before Visit 7, respectively (Table 19 and Table 20).

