8.3. Exploratory Efficacy Analyses

A Poisson regression model will be fit to estimate the rate of positive BV diagnoses through Visit 4 (Week 12) in each of the treatment arms and to compare the rate in the LACTIN-V arm to that in the placebo arm. The outcome of the model will be the number of positive BV diagnosis after enrollment and through Visit 4 and the model will include a covariate for treatment group and an offset term of log(follow-up time). The offset is included in the model as not all subjects will be followed up through Visit 4 (e.g. subjects who are lost to follow-up prior to Visit 4) and so subjects will have variable follow-up times. The follow-up time variable in the model will be the elapsed time (in days) from randomization to the earliest of the following: Visit 4 date, date of censoring from the particular analysis population, or the termination date. [Table 67](#) will present the treatment group-specific rates of BV (and 95% confidence interval) along with the rate ratio between treatment groups (and 95% confidence interval).

A repeated measures logistic regression model will be fit to estimate the odds of a positive BV diagnosis through Visit 4 (Week 12) in each of the treatment arms and to compare the odds of a BV diagnosis in the LACTIN-V arm to that in the placebo arm. The marginal model to be used will have covariates for treatment group, time, and a treatment by time interaction, i.e. the model is of the form:

$$g(E[Y_{ij}]) = \beta_0 + \delta_i\beta_1 + t_{ij}\beta_2 + \delta_it_{ij}\beta_3 + \epsilon_{ij}$$

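### In the ITT and mITT Kaplan-Meier and Poisson analyses, drop-outs are followed past their last BV exam, which modestly understates recurrence; the Kaplan-Meier paragraph also leaves censoring and imputation unreconciled

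*SAP*

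**What the plan says.** SAP 8.2 dates a recurrence at the midpoint between the first positive exam and the previous observed time point. A woman without recurrence is censored, with time running from first dose "to the Visit 4 time point, or to the first occurrence of loss to follow-up or the time-point at which the subject became ineligible". The Visit 7 version is defined in the same way. The paragraph then says the analyses are run in all four efficacy populations, "where the ITT and mITT summaries will be replicated using the imputation methods described in Section 6.5". Those methods are LOCF and a worst case in which missing LACTIN-V outcomes are failures and missing placebo outcomes are successes.

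SAP 4.3 describes loss to follow-up: women who do not return "after a minimum of three attempts to contact them over a 2-week period will be considered lost to follow-up". No analysis date is attached to that status.

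SAP 8.3 ends the Poisson follow-up time at the earliest of "Visit 4 date, date of censoring from the particular analysis population, or the termination date".

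BV exams are scheduled only at Weeks 4, 8, 12 and 24, with telephone contact at Weeks 16 and 20 (SAP 4.1). The protocol leaves the time-to-event details to the SAP (Protocol 11.6.4.1 and 11.6.4.2).

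**The concern.** A recurrence is normally established at an exam and is then dated back into the interval before it. A woman who leaves without a positive result should therefore stop contributing time at her last evaluable exam. Under the SAP wording she can contribute for weeks longer.

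Suppose her last exam is on Day 28 and she misses Visit 3 (target Day 56). Loss is declared no earlier than about Day 56 + 14 = Day 70, or Day 63 + 14 = Day 77 counting from the close of the window. She is then still in the risk set at Day 42, the midpoint of Days 28 and 56, and can be at Day 70, the midpoint of Days 56 and 84. No exam could have placed an event for her at either time. Between Visits 4 and 7 the unexamined gap is 84 days, with the event midpoint at Day 126. A woman reached by telephone on Day 140 who misses Visit 7 has passed that midpoint without a scheduled exam. The Poisson offset has the same feature.

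The result is that recurrence is understated in Figures 2-3, in the Table 18 quantiles and in the Table 67 rates.

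The second problem is one of specification. The paragraph codes a drop-out as censored and also calls for her to be imputed. It does not say which takes precedence or what time an imputed failure receives. The Table 17 shell has single ITT and mITT columns, whereas Table 11 has separate LOCF and worst-case rows.

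**Working it through.** **Planning inputs (SAP 5 and 6.1).** The proportion of controls "who will experience BV recurrence at 12 weeks is assumed to be 30"%, with a 50% reduction (so 15% on LACTIN-V), 2:1 allocation, 10% drop-out, two-sided 5% and 70% power.

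These reproduce the plan's sample size. The mean proportion is (0.30 + 2 × 0.15)/3 = 0.20.

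Placebo n = [1.960 × √(1.5 × 0.20 × 0.80) + 0.524 × √(0.30 × 0.70 + 0.15 × 0.85/2)]² / 0.15² = 67.7, so 68.

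The total is 3 × 68 = 204, and 204/0.9 = 227. The next multiple of 3 is 228, as stated.

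**Kaplan-Meier by Week 12, by hand.** Take equal risk in each exam interval: h = 1 − 0.70^(1/3) = 0.1121 on placebo and 1 − 0.85^(1/3) = 0.0527 on LACTIN-V. Let 5% of those still at risk leave after Visit 2 and 5% after Visit 3, and keep them in the risk set as the SAP wording allows. On placebo:

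- Interval 1: survival 1 − 0.1121 = 0.8879.
- Day 42: only 95% of the risk set can be examined, so the hazard is 0.95 × 0.1121 = 0.1065.
- Day 70: events are 0.8879 × 0.95 × 0.8879 × 0.95 × 0.1121 = 0.0798. The risk set is 0.8879 × 0.05 + 0.8879 × 0.95 × 0.8879 = 0.7934. The hazard is 0.1005.
- Estimate: 1 − 0.8879 × 0.8935 × 0.8995 = 28.6%, against a true 30%.

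The same steps on LACTIN-V give 14.3% against 15%. Removing leavers at their last exam restores the hazard h in every interval, and so 30% and 15%.

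**Kaplan-Meier by Week 24, by hand.** A constant hazard gives 1 − 0.70² = 51% on placebo. If 10% of those at risk at Day 126 go on to leave unexamined, the estimate is 1 − 0.70 × (1 − 0.9 × 0.30) = 48.9%.

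**Simulation.** This used constant recurrence hazard, exponential drop-out independent of BV, and midpoint event times. The ranges run from censoring at declared loss (missed contact plus 14 days) to censoring at the actual drop-out date. Drop-out is the proportion leaving by Day 84.

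| Drop-out | Week 12 placebo / LACTIN-V (true 30% / 15%) | Week 24 placebo / LACTIN-V (true about 51% / 28%) | Poisson rate relative to last-exam offset |
|---|---|---|---|
| 5% | 29.3–29.8% / 14.6–14.9% | 49.3–50.3% / 26.8–27.4% | 0.978–0.992 |
| 10% | 28.3–29.4% / 14.2–14.7% | 47.8–49.7% / 25.7–26.8% | 0.954–0.983 |
| 20% | 26.7–29.0% / 13.4–14.6% | 44.5–48.3% / 23.7–25.9% | 0.906–0.963 |

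Censoring at the last exam recovered the true values.

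**Poisson, least favourable timing.** Let every leaver be examined once (Day 28) and terminated on Day 77. At 10% drop-out the rate is multiplied by (0.9 × 84 + 0.1 × 28)/(0.9 × 84 + 0.1 × 77) = 78.4/83.3 = 0.941, a loss of about 6%.

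**Illustrative unequal drop-out, 20% placebo and 5% LACTIN-V.** The multipliers are 72.8/82.6 = 0.881 and 81.2/83.65 = 0.971. A true ratio of 0.50 becomes 0.50 × 0.971/0.881 = 0.55, or 0.45 with the arms reversed. The simulated timings give 0.51–0.54 and 0.46–0.49.

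**The case against.** The case for leaving the text alone has several good points.

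- **Population.** CC is primary for every efficacy outcome (SAP 6.1). CC and PP exclude early terminators with no positive result (SAP 6.3.2.3 and 6.3.2.4). This stands: a reader might infer that every panel of these tables is biased, but only the ITT and mITT versions are materially exposed. What can remain in CC and PP is small, such as Poisson time after a first positive.
- **Observation between exams.** SAP 6.3.2 counts withdrawal or product discontinuation for lack of effect, or starting other BV treatment, as recurrence at that time. Telephone visits can lead to an unscheduled exam (Protocol 7.6). An early-termination visit includes pH, wet mount and Gram stain (Protocol 7.9), and if done at exit it leaves no excess time. This stands as a limit on size. The visit is encouraged, not assured (Protocol 5.3.4).
- **What Table 17 shows.** Its shell gives a crude count, a median and quartiles, with no Kaplan-Meier proportion. At 30% and 15% neither median is reached. The placebo first quartile falls in the Day 70 cluster either way, since cumulative risk before it is 1 − 0.70^(2/3) = 21%. Table 17 therefore barely changes at Week 12 and the effect is seen in Figure 2. Table 18 is more sensitive: a placebo curve that truly reaches about 51% has a median, and one estimated at 47.8–49.7% does not. That 51% is an extrapolation absent from the documents.
- **Imputed runs.** A reader might infer that they cannot be produced at all. They can: LOCF is event-free time to the visit, and a worst-case failure can be given a midpoint. What is missing is the rule.

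**Conclusion.** The point holds, at modest size and in supportive analyses only. At 10% drop-out the understatement is about 0.3 to 1.7 points by Week 12, about 1 to 3 points by Week 24, and about 2 to 6% of the Poisson rate depending on when women leave. These figures assume 30% and 15% true recurrence, drop-out unrelated to BV and, for Week 24, a constant hazard carried beyond Week 12. The primary chi-square test is not affected.

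Two stronger readings are not supported. One is that the comparison between arms is biased in a known direction. SAP 5 gives 10% drop-out overall and nothing by arm, and equal drop-out leaves the rate ratio unchanged. The 20% and 5% split is an illustration: it moves a true 0.50 to roughly 0.51–0.55, or 0.45–0.49 if reversed. The other is that the imputation clause also understates recurrence. LOCF does (28.0% and 14.0% by Week 12 at 10% drop-out), but the worst case raises LACTIN-V recurrence from 15% to about 23%.

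The conflict between censoring and imputation is a separate gap. As written, two programmers could produce different Tables 17-18.

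**What to change.** - **SAP 8.2.** Censor a woman without recurrence at her last evaluable Amsel-plus-Nugent exam. State that the SAP 6.3.2 rule still applies, so lack-of-effect withdrawal or discontinuation, or starting other BV treatment, is a recurrence at that time.
- **SAP 8.3.** End the Poisson follow-up time at the same exam. Women with no post-dose exam and no SAP 6.3.2 event contribute no time.
- **Imputation, Tables 17-18 and Figures 2-3.** Either drop the clause, or state that imputed runs are separate sensitivity analyses with their own columns, with an imputed failure placed at the midpoint before the first missed visit.
- **Consistency.** The colonization Kaplan-Meier analysis in SAP 8.2 uses the same censoring wording and should be aligned.

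The clock change costs two sentences and a simpler derivation. The imputation rule costs one more sentence and, if the runs are kept, extra columns in the shells. No new data are needed, and all of it can be settled before unblinding.

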Women who develop *symptomatic* BV confirmed by wet mount Amsel criteria ≥ 3 (with or without confirmatory Gram stain) at least 4 weeks after the last MetroGel treatment will be retreated with MetroGel. This practice follows CDC treatment guidelines and FDA recommendations. The 5-day course of MetroGel will begin as soon as possible. Women will skip their regularly scheduled dose of study product until 24 hours after their last dose of MetroGel when study product dosing will continue twice weekly. Women diagnosed with *asymptomatic* BV during the follow-up visit will not be retreated with MetroGel.

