7.10 Unscheduled Visit

An unscheduled visit following a participant's request or the site investigator's recommendation should be recorded on the appropriate CRF. The following procedures and assessments may be performed at the unscheduled visit:

1. Staff will review the memory aid with the participant. The participant will be asked about symptoms, concomitant medications and any medical problems since the last visit, which will be recorded on the appropriate CRF. Additionally, the participant will be asked to provide exact dates and times of the study product administration.
2. Medical, gynecological and sexual history to include assessment of STI and HIV risk
3. Symptom-directed physical and pelvic examination by a study physician or nurse that will include vital signs, including temperature, and examination of respiratory and cardiovascular systems, as well as assessment of symptoms and adverse events
4. The pelvic examination will be conducted in the following order:
 - a. Examination of the external genitalia
 - b. Speculum insertion and examination of vagina, fornices and cervix with naked eye. Water will be used to ease speculum insertion. No lubricant should be used as it could contain chlorhexidine which may kill *Lactobacillus*.
 - c. Vaginal pH
 - d. Vaginal swab for wet mount taken from the posterior fornix for yeast vaginitis and clue cells and for amine test (whiff test)
 - e. Vaginal swab for Gram stain (Nugent scoring system)
 - f. Vaginal swabs (no more than two) for storage and future identification of vaginal bacteria, and possible multiomic (e.g. proteomics, metabolomics, etc.) testing
 - g. Vaginal swabs for *L. crispatus* identification with qPCR
 - h. If indicated, cervical (or vaginal) swab for nucleic acid amplification of *N. gonorrhoeae*, *C. trachomatis*, and *T. vaginalis*
 - i. Other tests as deemed necessary by the site investigator in response to symptoms presented at this visit
5. If indicated, clean catch urine dipstick; urinalysis if abnormal results indicate
6. If indicated, β hCG pregnancy test
7. All clinical and laboratory findings at the time of the evaluation will be recorded on the CRF. These findings will include observations present on the pelvic exam such

- as genital findings including location; presence or absence, and character of vaginal or cervical discharge or lesions; and results of any on-site tests.

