11.6.4.3 Analysis of Exploratory Efficacy Outcome

The statistical parameterizations of the exploratory objective will include, but are not limited to, the following:

- The number of positive BV diagnoses per 12 weeks of follow-up
- The probability of positive BV diagnoses during the 12 weeks of follow-up

For the first parameterization, a Poisson regression model will be fit to estimate the 12-week incidence of positive BV diagnoses in each of the treatment arms and to compare the incidence in the LACTIN-V arm to that in the placebo arm.

For the second parameterization, a repeated measures logistic regression model will be fit to estimate the probability of positive BV diagnoses in each of the treatment arms and to compare the probability of recurrence in the LACTIN-V arm to that in the placebo arm.

As the exploratory analyses include participants who received additional MetroGel treatment after experiencing symptomatic BV at a particular follow-up visit, a sensitivity analysis will be performed to assess the effect of the additional treatment on the outcome. Details of the sensitivity analysis will be provided in the Statistical Analysis Plan.

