3.3. Study Definitions and Derived Variables

3.3.1. BV Diagnosis

The Amsel criteria and Nugent score will be used to diagnose BV.

During a pelvic examination, presence of the following Amsel criteria will be determined:

- a. Homogeneous, thin, grayish-white discharge that smoothly coats the vaginal walls
- b. Vaginal pH > 4.5
- c. Positive whiff-amine test, defined as the presence of a fishy odor when a drop of 10% potassium hydroxide (KOH) is added to a sample of vaginal discharge
- d. Presence of clue cells (>20%) on microscopy

A vaginal swab for assessment of BV by Nugent criteria will be performed. The Nugent score utilized a 0-10-point scale for evaluation of vaginal flora. The Nugent score is interpreted as follows:

- 0-3 Normal
- 4-6 Intermediate
- 7-10 BV

A positive diagnosis of BV is defined by the presence of at least three of the Amsel criteria and a Nugent score of 4 or greater.

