6.3.2. Efficacy Analyses

All efficacy analyses will be performed in the Intent-to-Treat, Modified Intent-to-Treat, Complete Case, and Per Protocol analysis populations. For analyses of cumulative BV recurrence at Visit 4 or Visit 7 in all efficacy populations, subjects who withdraw or are withdrawn from study participation prior to the visit of interest and the reason for withdrawal recorded on the CRF is lack of treatment effect are included in the analysis population as experiencing recurrent BV at the point in time of the withdrawal. Likewise, for analyses of cumulative BV recurrence at Visit 4 or Visit 7 in all efficacy populations, subjects who discontinue study product prior to the visit of interest and the reason for discontinuation recorded on the CRF is lack of treatment effect or begin other treatment for BV prior to the visit of interest are included in the analysis population as experiencing recurrent BV at the point in time of the discontinuation or commencement of the other treatment.

See Section 6.5 for the imputation methods that will be used in the efficacy analyses.

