8. EFFICACY EVALUATION

8.1. Primary Efficacy Analysis

For the primary analysis, the cumulative proportion of BV recurrence by Visit 4 (Week 12) will be summarized by treatment group. A formal hypothesis test will be performed with null hypothesis that the cumulative proportion of BV recurrence by Visit 4 (Week 12) in the LACTIN-V group is equal to that in the placebo group and alternative hypothesis that they are not equal. Cumulative proportion of BV recurrence is defined as follows: the numerator is the number of subjects who experience recurrence at least once through Visit 4 in the particular analysis population and the denominator is the number of subjects included in the particular analysis population. [Table 11](#) will present the cumulative proportion of BV recurrence by Visit 4 (Week 12) (and 95% Wilson confidence interval) in each treatment group along with the odds ratio of BV recurrence proportions between treatment groups (and 95% asymptotic confidence interval). The p-value from the Chi-Square test will be presented. The summaries will be calculated in the ITT, mITT, CC, and PP populations, where the ITT and mITT summaries will be replicated using the imputation methods described in Section 6.5. [Listing 6](#) will present individual efficacy data for all subjects.

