8.2. Secondary Efficacy Analyses

[Table 12](#) will present the cumulative proportion of BV recurrence by Visit 7 (Week 24) (and 95% Wilson confidence interval) in each treatment group along with the odds ratio of BV recurrence proportions between treatment groups (and 95% asymptotic confidence interval). A formal hypothesis test will be performed with null hypothesis that the cumulative proportion of BV recurrence by Visit 7 (Week 24) in the LACTIN-V group is equal to that in the placebo group and alternative hypothesis that they are not equal. The p-value from the Chi-Square test will be presented. The summaries will be calculated in the ITT, mITT, CC, and PP populations, where the ITT and mITT summaries will be replicated using the imputation methods described in Section 6.5. [Table 13](#), [Table 14](#), [Table 15](#), and [Table 16](#) will present BV recurrence by study visit (Day 28, 56, 86, and 168). For the by-visit summaries, the proportions of subjects with BV recurrence at a visit is defined as follows: the numerator is the number of subjects who experience recurrence at the particular visit and the denominator of the proportion of subjects with BV recurrence is the number of subjects in the analysis population who returned for the visit. The 95% Wilson confidence interval for the proportion in each treatment group along with the odds ratio of BV recurrence proportions between treatment groups (and 95% asymptotic confidence interval) and the p-value from the Chi-Square test will also be presented.

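### SAP Tables 19-20 check the influence of re-treatment by deleting re-treated women, who are all or nearly all recurrences, so the analysis selects on the outcome

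*SAP*

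**What the plan says.** SAP 8.2 labels Tables 19 and 20 a sensitivity analysis of recurrence by Visit 4 and by Visit 7. The cumulative analysis is repeated "after removing the subjects who received additional treatment for BV as documented in the concomitant medications CRF", where that treatment fell after the first dose and before the visit concerned.

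Three other rules determine who is removed:

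- **Who is re-treated.** Protocol 7.3 (repeated in 7.5, 7.8 and 7.10) says women with symptomatic BV and Amsel of at least 3, "with or without confirmatory Gram stain) at least 4 weeks after the last MetroGel treatment will be retreated with MetroGel". Asymptomatic BV is not re-treated.
- **How treatment is coded.** SAP 6.3.2 says that in the cumulative analyses women who "begin other treatment for BV prior to the visit of interest are included in the analysis population as experiencing recurrent BV".
- **What counts as an event.** SAP 3.3.1 says a positive diagnosis is "defined by the presence of at least three of the Amsel criteria and a Nugent score of 4 or greater". In SAP 8.1, "the numerator is the number of subjects who experience recurrence at least once through Visit 4".

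Neither *other* treatment (6.3.2) nor *additional* treatment (8.2) is defined, so it is unclear whether either term covers protocol MetroGel.

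For the exploratory repeated-episode models, protocol 11.6.4.3 commits to a sensitivity analysis for additional MetroGel and adds: "Details of the sensitivity analysis will be provided in the Statistical Analysis Plan".

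**The concern.** A woman is normally re-treated because she has recurred. Removing re-treated women therefore takes cases out of the numerator and leaves the non-cases in the denominator. Recurrences that were asymptomatic, or first found at the visit of interest, also stay in. What remains is a comparison of the recurrences that escaped treatment.

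The endpoint is at least one recurrence, so treatment given after the first one cannot reverse it. The useful question is whether the result depends on counting women as recurrent because they were treated without a confirmed diagnosis. Deletion cannot answer that, because it discards the confirmed recurrences as well.

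The study report would then carry odds ratios and p-values, presented as a check on the recurrence outcomes, that could make a real effect look fragile or lend support to a null one. Two linked gaps add to this:

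- **Populations.** The 8.2 text names mITT and CC for these tables, while the Table 19 shell has rows for CC and PP.
- **Exploratory models.** Re-treatment can change later episodes in these models, yet SAP 8.3 contains no such sensitivity analysis and SAP 13 does not list its omission.

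**Working it through.** **Who is removed.** If *other* treatment includes protocol MetroGel, every removed woman is an event by SAP 6.3.2. If it does not, the exceptions are women treated on Amsel of at least 3 whose Nugent score was below 4 or unavailable. Protocol 2.2.1 suggests few would score below 4: it describes Amsel of three or more as correlating with Gram stain and reports that, in the Phase II-a data, Amsel 4 always came with Nugent 8 or higher.

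**Design figure reproduced.** Inputs from SAP 5 and 6.1: placebo 30%, LACTIN-V 15%, 2:1 allocation, two-sided 5%, Pearson chi-square, 70% power, 10% drop-out. The usual two-proportion formula without continuity correction gives 68 placebo and 204 in total. Then 204/0.9 = 226.7, so 227, or 228 as a multiple of 3, which matches the plan. Evaluable: 228 × 0.9 ≈ 205, that is 68 and 137. Expected events: 68 × 0.30 + 137 × 0.15 = 20.4 + 20.55 = 40.95. OR = (0.15/0.85)/(0.30/0.70) = 0.412.

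**Effect of deletion.** Let f be the share of an arm's recurrences that is removed.

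- Remaining proportion: p(1−f)/(1−pf), on n(1−pf) women.
- The arm's odds are multiplied by (1−f), so OR = 0.412 × (1−f_L)/(1−f_P).
- Power: pooled-null normal approximation to the chi-square test, both tails.

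Example with f = 0.50 in both arms: placebo 0.15/0.85 = 17.6% of 57.8 women; LACTIN-V 0.075/0.925 = 8.1% of 126.7 women.

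The documents give no value for f, so it is an assumed range. Recurrences first found at Visit 4 cannot be removed from Table 19. If recurrences spread evenly over Visits 2 to 4 (assumption), f cannot exceed 67%.

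| True rates (placebo/LACTIN-V) | f placebo/LACTIN-V | OR | Events removed | Power or rejection |
|---|---|---|---|---|
| 30/15% | 0/0% | 0.412 | 0 | 70.3% |
| 30/15% | 25/25% | 0.412 | 10.2 | 60.9% |
| 30/15% | 50/50% | 0.412 | 20.5 | 48.4% |
| 30/15% | 67/67% | 0.412 | 27.3 | 37.8% |
| 30/15% | 50/25% | 0.618 | 15.3 | 21.3% |
| 30/15% | 25/50% | 0.275 | 15.4 | 84.0% |
| 30/30% | 25/50% | 0.667 | 25.7 | 19.5% |
| 30/30% | 50/25% | 1.50 | 20.5 | 16.1% |
| 30/30% | 40/50% | 0.833 | 28.7 | 7.8% |

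Simulation of the chi-square test agrees to within about 1.3 percentage points throughout.

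**Does the reading of *other* matter?** Suppose 10% of removed women are non-events (assumption). The 50/25% case gives OR 0.606, the 25/50% case 0.274, and the null 25/50% case 0.675 with 18.6% rejection. The result hardly changes.

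**Alternative: keep everyone and re-score.** Let a share u of re-treated women be scored non-recurrent, so the proportion becomes p(1−uf) on the full denominator. With u = 0 the OR is 0.412. For f of 50/50%, 50/25% and 25/50%, the OR is 0.417, 0.430 and 0.402 at u = 10%, and 0.422, 0.449 and 0.392 at u = 20%. With no true effect and unequal shares, rejection is 5.1% to 5.7%.

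**The case against.** The case on the other side has several parts.

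- **Purpose.** SAP 8.2 does not say what Tables 19-20 are for. They could be meant to show whether the treatment-as-event rule in 6.3.2 carries the result. The purpose is indeed inferred from the label and the table title. On that reading too, deletion fails, because it removes confirmed recurrences along with the treatment-coded ones.
- **Stakes.** These are supplementary tables in a Phase II-b screening trial, beside six analyses in Table 11. This stands, and it limits the severity.
- **Unequal shares are speculative.** Masking and a single re-treatment rule apply to both arms, and with equal shares the OR is unbiased. The documents show no difference in shares. Nothing ensures equality either: it fails if the product changes how often a recurrence is symptomatic. Even with equal shares, events and power are lost.
- **67% is extreme.** Re-treatment needs symptoms and four weeks since the last MetroGel, while Visit 2 may fall from Day 21. That is fair; 67% is a ceiling. The effect on Table 20 has not been quantified.
- **Other tables already cover it.** By-visit Tables 13-16 keep re-treated women, since "the denominator of the proportion of subjects with BV recurrence is the number of subjects in the analysis population who returned for the visit", but they do not address the cumulative endpoint. Tables 17-18 might be read as counting diagnoses only, but 6.3.2 dates treatment-coded recurrences at the start of treatment, so that reading is not secure.
- **The blinded case review could censor re-treated women.** It decides case by case and is not a pre-specified sensitivity analysis.
- **Re-scoring adds little.** One of the two scorings will nearly repeat Table 11. That is what a sensitivity analysis shows when the primary result does not hinge on the rule.

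**Conclusion.** The concern holds and should be fixed. Tables 19-20 remove all or nearly all re-treated women as events, so they select on the outcome and cannot show whether re-treatment drives the result. With equal re-treated shares of 25% to 67%, the OR stays at 0.41 while power falls to between 61% and 38%. With a twofold gap in shares, the OR moves to 0.62 or 0.27, and rejection under no effect rises to 16-19%; a 40/50% gap gives about 8%. All of this rests on the design rates and on assumed shares. The structural point does not depend on those values. The primary analysis in Table 11 is untouched. The population mismatch and the missing exploratory sensitivity analysis are plain discrepancies in the text.

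**What to change.** 1. Replace the deletion in Tables 19-20 with an analysis that keeps all women in the denominator and changes only the scoring of re-treated women: (a) all re-treated women recurrent; (b) recurrent only if Amsel is at least 3 and Nugent at least 4 at some visit through the visit of interest. In (b), do not score as non-recurrent by default women treated without evaluable Amsel and Nugent results at or before treatment. This can arise at unscheduled visits, where protocol 7.10 says "The following procedures and assessments may be performed at the unscheduled visit". Keep these women as recurrent or show both scorings.
2. State whether *other* treatment in 6.3.2 and *additional* treatment in 8.2 include protocol MetroGel.
3. Use the same populations in the 8.2 text and the Table 19-20 shells.
4. Either add to SAP 8.3 the re-treatment sensitivity analysis promised in protocol 11.6.4.3, or list its omission in SAP 13. One option is to end follow-up at first re-treatment and keep the diagnosing visit, with the caveat that this conditions on a post-randomization event and drops later episodes.

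The cost is SAP wording, two table shells and one derived variable. Listing 6 (Amsel, Nugent and diagnosis by visit) and Listing 17 (concomitant medications) already hold the inputs. Data collection does not change.
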